4.0 STUDY ACTIVITIES AND ASSESSMENTS

The schedule of events is provided in Appendix 5. Descriptions of the scheduled evaluations are outlined below and complete information on study drug and dosing is provided in Section 3.5.

Before study entry, throughout the study, and at the follow-up evaluation, various clinical and diagnostic laboratory evaluations are required. The purpose of obtaining these detailed measurements is to ensure adequate safety and tolerability assessments. Clinical evaluations and laboratory studies may be repeated more frequently if clinically indicated. Such unscheduled assessments will be captured in the protocol-specific database as appropriate.

4.1 DESCRIPTION OF PROCEDURES

4.1.1 Informed Consent

The subject must read, understand and sign the IRB/IEC approved ICF confirming his or her willingness to participate in this study before initiating any screening activity that is not standard of care. Subjects must also grant permission to use protected health information.

4.1.2 Medical History

The subject's complete history should be collected and recorded through review of medical records and by interview. Concurrent medical signs and symptoms must be documented to establish baseline severities. A disease history, including the date of initial diagnosis and list of all prior anticancer treatments, and responses and duration of response to these treatments, also will be recorded.

4.1.3 Adverse Events

The accepted regulatory definition for an AE is provided in Section 6.1 All medical occurrences from the time of first dose that meet this definition must be recorded. Important additional requirements for reporting SAEs are explained in Section 6.2.

4.1.4 Concomitant Medications and Therapy

All concomitant medications and procedures from within 21 days before the start of study drug administration through 30 days after the last dose of study drug should be documented.

4.1.5 Confirmation of Eligibility

Subject eligibility for enrollment will be assessed per Section 3.4. All screening procedures, unless otherwise indicated, should be completed within 21 days of the first dose of study drug.

4.1.6 ECOG Performance Status

The ECOG performance index is provided in Appendix 1.

4.1.7 Physical Examination, Vital Signs, Height & Weight

The screening physical examination will include, at a minimum, the general appearance of the subject, height (screening only) and weight, and examination of the skin, eyes, ears, nose, throat, lungs, heart, abdomen, extremities, musculoskeletal system, nervous system, and lymphatic system.

Symptom-directed physical exams, including tumor assessments by palpation, will be done during the treatment period and at the safety follow-up visits.

Vital signs (blood pressure, heart rate, respiratory rate, and body temperature) will be assessed after the subject has rested in the sitting position.

4.1.8 Bone Marrow Aspirate and Biopsy

A bone marrow aspirate and biopsy will be done at screening or up to 30 days before the main screening procedures. Per the current response criteria (Rajkumar 2011), a bone marrow aspirate/biopsy will also be required at any time on study to confirm a complete response (CR). The baseline bone marrow aspirate/biopsy will used for immunohistochemistry and/or flow cytometry, cytogenetics, and FISH. Testing will be performed at the study center's local laboratory or other clinical laboratory listed on the investigator's form FDA 1572. De-identified copies of all bone marrow biopsy/aspirate results may be requested by the sponsor.

When available, any unused bone marrow tissue will be used for PD testing. PD testing will be done by the sponsor.

4.1.9 Electrocardiogram

Subjects should be in supine position and resting for \geq 10 minutes before study-related ECGs.

4.1.10 Urine Pregnancy Test

Pregnancy tests will be required only for women of childbearing potential. If positive, pregnancy must be ruled out by ultrasound. Testing will be done by the central laboratory.

4.1.11 Hematology

Hematology studies must include complete blood count (CBC) with differential and platelet and reticulocyte counts. Testing will be done by the central laboratory.

4.1.12 Serum Chemistry

Serum chemistry must include albumin, alkaline phosphatase, ALT, AST, bicarbonate, blood urea nitrogen (BUN), bone-specific alkaline phosphatase, calcium, chloride, creatinine, C-terminal telopeptide, glucose, lactate dehydrogenase (LDH), magnesium, phosphate, potassium, sodium, total bilirubin, total protein, and uric acid. If an unscheduled ECG is done at any time, then an electrolyte panel (ie, calcium, magnesium, and potassium) must be done to coincide with the ECG testing. Testing will be done by the central laboratory.

4.1.13 Urinalysis

Urinalysis includes pH, ketones, specific gravity, bilirubin, protein, blood, N-terminal telopeptide, and glucose. Testing will be done by the central laboratory.

4.1.14 T/B/NK Cell Count

Flow cytometry testing will include CD3⁺, CD4⁺, CD8⁺, CD19⁺, and CD16/56⁺ cells. Testing will be done by the central laboratory.

4.1.15 Disease Markers

Testing for serum M-protein levels (by serum protein electrophoresis [SPEP] and serum immunofixation electrophoresis [SIFE]), serum free light chains (SFLC), urine M-protein levels (by urine serum protein electrophoresis [UPEP] and urine immunofixation electrophoresis [UIFE]), and serum β 2-microglobulin will be done by the central laboratory.

4.1.16 Skeletal Survey

Standard lateral radiograph of the skull, anterioposterior and lateral views of the spine, and anterioposterior views of the pelvis, ribs, femora, and humeri are required at screening or baseline (ie, before the first dose of study drug). Radiographic imaging and analysis will be performed at the study center's local laboratory or other clinical laboratory listed on the investigator's form FDA 1572.

4.1.17 Pharmacodynamics

Blood samples and bone marrow, when available, will be used for PD testing (eg, Btk occupancy and B-cell activation). Refer to the laboratory binder for instructions on collecting and processing these samples. Testing will be done by the sponsor.

4.1.18 Pharmacokinetics

Refer to the laboratory binder for instructions on collecting and processing these samples. Testing will be performed at the central clinical laboratory. Leftover plasma samples may be used for exploratory ACP-196 metabolite analyses. The PK sampling timepoints are provided in Table 4-1.

					HOURS P	OSTDOSE		
Cycle	Day	Predose	0.5 (±5 min)	0.75 (±5 min)	1 (±5 min)	2 (±10 min)	4 (±10 min)	6 (±10 min)
1	1	Х	Х	Х	Х	Х	Х	Х
	8	Х			Х			
	15	Х			Х			
	22	Х	Х	Х	х	Х	Х	Х
	28	Х			Х			

 Table 4-1. Pharmacokinetic Sample Schedule

Note: These timepoints are relative to the morning dose.

4.1.19 Tumor Assessment

Baseline myeloma assessments will consist of:

- M-protein determination using both of the following procedures:
 - serum protein electrophoresis (SPEP) and serum immunofixation electrophoresis (SIFE)

- Urine protein electrophoresis (UPEP) and urine immunofixation electrophoresis (UIFE), all using the same 24-hour urine collection
- SFLC
- Plasmacytoma evaluation
- Bone marrow to quantify percent myeloma cell involvement (aspirate and biopsy required at baseline)
- Skeletal survey: lateral radiograph of the skull, anterioposterior and lateral views of the spine, and anterioposterior views of the pelvis, ribs, femora, and humeri
- β2-microglobulin

On-study myeloma assessments will consist of:

- SPEP and/or UPEP (if results were measurable at baseline); quantitative immunoglobulins if used to follow disease; immunofixation to confirm a complete response
- SFLC
- Plasmacytoma evaluation (if only measurable disease at baseline)
- Bone marrow aspirate and/or trephine bone biopsy (to confirm a complete response or if clinically indicated).

4.1.20 Study Drug Accountability

See Section 7.7.

4.2 INVESTIGATOR'S ASSESSMENT OF RESPONSE TO TREATMENT

Subjects will be evaluated by investigator review for disease response and progression according to the current guidelines proposed by the International Myeloma Workshop Consensus Panel 1 (Rajkumar 2011) and European Group for Blood and Marrow Transplant (EBMT; Bladé 1998)as listed below in . Response categories include sCR, CR, VGPR, PR, SD, and progressive disease. In addition, the number of subjects achieving the response category of MR will also be evaluated and reported. Subjects will be considered evaluable for response if they have a baseline and \geq 1 adequate onstudy myeloma assessment obtained \geq 4 weeks from the start of therapy.

Table 4-2, Re	sponse Criteria (de	rived from Raikumar	r 2011 and	Bladé 1998)

Response Subcategory	Response Criteria ^a
Complete response (CR)	Negative immunofixation of serum and urine and
	Disappearance of any soft tissue plasmacytomas and
	 < 5% plasma cells in bone marrow^b.
Stringent complete	CR as defined above plus
response (sCR)	Normal FLC ratio and
	 Absence of clonal plasma cells by immunohistochemistry or 2- to 4-color flow cytometry.
Very good partial response (VGPR)	Serum and urine M-component detectable by immunofixation but not on electrophoresis or
	 ≥ 90% reduction in serum M-component plus urine M-component < 100 mg per 24 h.
Partial response (PR)	• ≥ 50% reduction of serum M-protein and reduction in 24-h urinary M-protein by ≥ 90% or to < 200 mg per 24 h
	 If the serum and urine M-protein are not measurable, a ≥ 50% decrease in the difference between involved and uninvolved FLC levels is required in place of the M-protein criteria
	 If serum and urine M-protein are not measurable, and serum free light assay is also not measurable, ≥ 50% reduction in bone marrow plasma cells is required in place of M-protein, provided baseline percentage was ≥ 30%
	 In addition to the above criteria, if present at baseline, ≥ 50% reduction in the size of soft tissue plasmacytomas is also required
Minimal response (MR)	 Requires all of the following: ≥ 25% to ≤ 49% reduction of serum M-protein and 50% to 89% reduction in 24-hour urine M-protein and If present at baseline, 25-49% reduction in the size of soft tissue plasmacytomas and No increase in size or number of lytic bone lesions (development of compression fracture does not exclude response).
Stable disease (SD)	Not meeting criteria for CR, VGPR, MR, PR or progressive disease
Progressive disease	Any of the following:
	 Increase of ≥ 25% from lowest response value^c in:
	• Serum M-component (absolute increase must be $\geq 0.5 \text{ g/dL})^d$
	 Ourine M-component (absolute increase must be ≥ 200 mg/24 h)

Acerta Pharma

	 Only in subjects without measurable serum and urine M-protein levels: the difference between involved and uninvolved FLC levels (absolute increase must be > 10 mg/dL)
	 Only in subjects without measurable serum and urine M- protein levels and without measurable disease by FLC levels bone marrow plasma cell percentage (absolute increase must be ≥ 10%)
•	Definite development of new bone lesions or soft tissue plasmacytomas or definite increase in the size of existing bone lesions or soft tissue plasmacytomas
•	Development of hypercalcemia (corrected serum calcium > 11.5 mg/dL) that can be attributed solely to the plasma cell proliferative disorder

Abbreviations: FLC = (serum) free light chains

Note: in subjects in whom the only measurable disease is by serum FLC levels, CR requires a normal FLC ratio of 0.26-1.65 in addition to negative serum and urine immunofixation. VGPR in such subjects is defined as a > 90% decrease in the difference between involved and uninvolved free light chain FLC levels

- a. All response categories (CR, sCR, VGPR, PR, and PD) require 2 consecutive assessments made at ≥4 weeks after the start of study therapy and any time before the institution of any new therapy after study therapy; CR, sCR, VGPR, PR, and SD categories also require no known evidence of progressive or new bone lesions if radiographic studies were performed. VGPR and CR categories require serum and urine studies regardless of whether disease at baseline was measurable on serum, urine, both, or neither. Radiographic studies are not required to satisfy these response requirements.
- b. Bone marrow assessments need not be confirmed.
- c. Lowest response value does not need to be a confirmed value.
- d. For progressive disease, serum M-component increases of ≥ 1 gm/dL are sufficient to define relapse if starting M-component is ≥ 5 g/dL.

4.3 EARLY TERMINATION/SAFETY FOLLOW-UP VISIT

An early termination visit is required for any subjects who permanently discontinue study drug early for any reason including disease progression. Each subject should be followed for 30 (±7) days after his or her last dose of study drug (ie, the "safety follow-up visit") to monitor for resolution or progression of AEs (see Section 6.2.5) and to document the occurrence of any new events; unless, the subject receives a new anticancer therapy within this timeframe. Subjects who withdraw consent should still be encouraged to complete the safety follow-up assessments, but these assessments cannot be mandated once consent is withdrawn. The Schedule of Assessments (Appendix 5) describes the procedures required for the safety follow-up.

4.4 MISSED EVALUATIONS

Missed evaluations should be rescheduled and performed as close to the original scheduled date as possible. An exception is made when rescheduling becomes, in the

investigator's opinion, medically unnecessary or unsafe because it is too close in time to the next scheduled evaluation. In that case, the missed evaluation should be abandoned.

5.0 STATISTICAL METHODS OF ANALYSIS

5.1 GENERAL CONSIDERATIONS

Descriptive statistics (including means, standard deviations, and medians for continuous variables and proportions for discrete variables) will be used to summarize data as appropriate. Analyses will be done by dosing regimen and overall.

5.2 SAMPLE SIZE CONSIDERATIONS

This study will assess safety, PK, PD, and antitumor activity of ACP-196 alone or in combination with dexamethasone. Subjects will be equally randomized into 1 of the 2 dosing regimens (ACP-196 monotherapy or ACP-196 + dexamethasone) as an efficient method for allocating patients into these regimens. The study is not formally designed to compare these regimens but rather to obtain descriptive information that can be used in support of further ACP-196 development.

While the primary objective of this study is to determine the safety in each of the 2 dosing cohorts, the sample size has been determine to independently evaluate the activity of each dosing regimen. The trial seeks to exclude an uninteresting ORR of $\leq 15\%$ (ie, the response rate that might be associated with single-agent dexamethasone therapy [Anderson 2013]) in favor a target response rate of $\geq 40\%$. Considering a sample size of 19 subjects per cohort, the power to detect the difference between a null-hypothesis response rate of 15% and an alternative-hypothesis response rate of 40% with a 0.025 one-sided significance level is 69% using a one-group, exact binomial test. A sample size of 19 subjects per cohort will also provide a 97.5% 1-sided confidence interval centered around an expected ORR of 40% that excludes an ORR of 18.6% as a lower bound.

5.3 DEFINITION OF ANALYSIS POPULATIONS

The following definitions will be used for the analysis populations:

- Safety population: All enrolled subjects who receive ≥ 1 dose of study drug.
- Intent-to-treat (ITT) population: All subjects who have been randomized.

The safety population will be used for evaluating the safety parameters in this study. The ITT population will be analyzed for efficacy parameters in this study.

Acerta Pharma

5.4 MISSING DATA HANDLING

General Considerations: Subjects lost to follow-up (or who dropped out) will be included in statistical analyses up to the point of their last evaluation.

Duration of Response and Progression-free Survival: Data for subjects without disease progression or death will be censored at the date of the last tumor assessment and before the initiation of alternative anticancer therapy.

Safety: Missing or partial start and end dates for AEs and concomitant medications will be imputed according to prespecified, conservative imputation rules. No other imputation of values for missing data will be performed.

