6.2.1 Adverse Event Reporting Period

The AE reporting period for this study begins when the subject receives the first dose of study medication and ends with the safety follow-up visit (or last on-treatment visit if the safety follow-up visit is not done), or when the subject receives a new anticancer therapy. An exception to this reporting period is any AE occurring due to a protocol-defined screening procedure. Fatal AEs occurring within 30 days after the last dose of ACP-196 **AND** assessed by the investigator as related to ACP-196 must be reported as a SAEs.

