## **1. INTRODUCTION**

The purpose of this statistical analysis plan (SAP) is to provide details of the safety and efficacy analyses that have been outlined within Protocol Amendment 2 for Study ACE-MY-001, which is entitled “An Open-label, Phase 1b Study of ACP-196 in Subjects with Multiple Myeloma” dated January 13, 2016. The original SAP based on same protocol was for interim safety clinical study report (CSR) to support the new drug application (NDA) in relapsed and refractory mantle cell lymphoma. This SAP is updated to include efficacy analysis. Any change to the planned analyses described in the final SAP will be documented in the clinical study report (CSR).

Separate reports will be generated for pharmacokinetic (PK) and pharmacodynamic (PD) data.

From here on, acalabrutinib (generic name for formerly ACP-196) will be used in place of ACP-196 in this document.

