## **9. MISSING VALUES**

### **Missing Safety Data**

Conservative imputation rules will be applied partial dates for AE onset and stop dates, start and end dates of concomitant medication, start date of subsequent anticancer therapy, date of initial diagnosis, and death date. The algorithm for the imputation in Appendices 14.2 will be used. If dates are completely missing, no imputation will be made. Missing safety data other than partial or missing dates will not be imputed.

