### 10.5.2 Prior and Concomitant Medications Received for Indications Other Than MM

Concomitant therapy is defined as all medications used on or after the first dose of study drug, through the treatment phase, and through 30 days following the last dose of study drug. Data reported on concomitant medications CRF pages will be used. Medications

started prior to first dose of study drug will be considered as prior treatment. Using this definition, a medication can be classified as both prior and concomitant. The start date and end date will be based on the rules provided in [Appendices 14.2.1](#). Medications with completely missing start and stop dates will be considered as both prior and concomitant medications. Prior and concomitant medications other than antineoplastic agents or other systemic therapies for MM after enrollment will be coded by the World Health Organization (WHO) Drug Dictionary and summarized by Anatomic Therapeutic Chemical Classification System (ATC) level 2 (therapeutic subgroup) and level 5 (preferred term/chemical ingredient).

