### 10.6 Analyses of Safety Endpoints

Safety analyses will be performed on All-treated population by treatment cohort.

Analyses of adverse events (AEs) will be performed on treatment-emergent AE (TEAE) data, unless otherwise specified. TEAEs are defined as those events with onset or

worsen date on or after the date of first dose of acalabrutinib, through the treatment phase to last dose of acalabrutinib, and within 30 days following the last dose of acalabrutinib, whichever is later. Common Terminology Criteria for Adverse Events (CTCAE) Version 4.03 or higher is used for AE grading.

Treatment-emergent AEs will be summarized in 3 groups: (1) acalabrutinib monotherapy, (2) acalabrutinib + dexamethasone, and (3) crossover from monotherapy to acalabrutinib + dexamethasone therapy. By this grouping method, AEs among subjects assigned to acalabrutinib monotherapy will be reported in group 1 when AEs occurred before crossover, and AEs occurred on/after crossover will be reported in group 3. Treatment-emergent AEs occurred on or after crossover will be summarized in the crossover group. Treatment-emergent AEs occurred before crossover will be summarized in the monotherapy group. All AE terms will be coded by Medical Dictionary for Regulatory Activities (MedDRA) Version 19.1 and will be presented by system organ class (SOC) and preferred term (PT). Treatment-emergent AEs will be summarized by SOC and PT and by CTCAE toxicity grade. The drug-related AEs, serious adverse events (SAEs) and drug-related SAEs, AEs leading to treatment discontinuation, dose delay and dose modification will be summarized by PT by CTCAE toxicity grade.

Death will be reported in a listing and summarized. A table will be provided for grade 5 AE and the relationship with any study drug.

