### 14.2 Imputation Rules

#### 14.2.1 Partial or Missing Dates

Imputation of partial dates will be made for AE onset and stop dates, start and end dates of concomitant medication, start date of subsequent anticancer therapy, date of initial diagnosis and death date. If dates are completely missing, no imputation will be made. For any partial date with missing year, no imputation will be made.

The general rule for imputation is:

- If only day is missing, then the 15th of the month will be used.
- If only year is present, then June 30th will be used.

If such imputation date for initial diagnosis is on or after date of first dose, the date of first dose – 1 will be used. If such imputed date for subsequent anticancer therapies is before date of last dose, the date of last dose + 1 will be used.

If the imputed date is for an AE start date and is in the same year and month as the first dose date but before the first dose date, the first dose date will be used, or if the imputed AE start date is after the AE end date, the AE end date will be used. If the imputed date is for an AE start date and is in the same year and month as but after the last dose date + 30 days, the last dose date + 30 days will be used.

If the imputed date is for an AE end date and is after the death date, the date of death will be used, or if the imputed AE end date is before the AE start date, the AE start date will be used.

If death year and month are available but day is missing:

- If mmyyyy for last contact date = mmyyyy for death date, set death date to the day after the last contact date.
- If mmyyyy for last contact date < mmyyyy for death date, set death date to the first day of the death month.
- If mmyyyy for last contact date > mmyyyy for death date, data error and do not impute.

If both month and day are missing for death date or a death date is totally missing, no imputation is made.

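### An adverse event with no usable onset date cannot count as treatment-emergent under the SAP, although Protocol 5.4 promises conservative imputation of missing dates

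*Protocol*

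**What the plan says.** **Protocol.** Section 5.4 covers both classes of incomplete date: "Missing or partial start and end dates for AEs and concomitant medications will be imputed according to prespecified, conservative imputation rules". The SAP introduction says that it details the analyses "outlined within Protocol Amendment 2 for Study ACE-MY-001", so the Amendment 2 text of 5.4 controls; the Amendment 1 copy reads the same. Section 6.2.1 fixes when AE collection starts: "The AE reporting period for this study begins when the subject receives the first dose of study medication". The one exception is an AE caused by a protocol-defined screening procedure.

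**SAP, imputation.** Section 9 (Missing Safety Data) describes its rules as conservative but applies them to partial dates. It then states "If dates are completely missing, no imputation will be made". Appendix 14.2.1 repeats this and adds "For any partial date with missing year, no imputation will be made". A date with only the day missing becomes the 15th of the month, and a date with only the year becomes 30 June. An imputed AE start that falls before first dose is moved to first dose only when it shares both the year and the month of first dose.

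**SAP, classification.** Section 10.6 runs AE analyses on TEAEs unless otherwise specified: "TEAEs are defined as those events with onset or" "worsen date on or after the date of first dose of acalabrutinib", up to 30 days after the last dose. It also splits events in monotherapy subjects into those before crossover and those on or after it.

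**SAP, the parallel case.** For medications there is a default: "Medications with completely missing start and stop dates will be considered as both prior and concomitant medications". No such default is given for AEs. Section 12 reports no major change from the protocol's analyses.

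**The concern.** Safety is the primary objective (Protocol 2.1, SAP 2.1), and the TEAE tables are its main output. The protocol says that an AE with a missing date will be given one by a conservative rule. The SAP gives it none, then uses the date to decide whether the event counts. Because AE recording starts at first dose, an AE with no onset date is very likely to have begun on treatment. Leaving it unclassified therefore works against a conservative safety summary, and the reader of the SAP is not told that the protocol's method was changed. In cohorts planned at 20 subjects, with enrolment stopped early (SAP 3.1), a single subject is visible in a table row.

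**Working it through.** No stated figure in the plan depends on this point. The check is to apply the SAP's rules literally and then size one lost subject.

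**1. Compare the two texts.** Protocol 5.4 imputes missing and partial AE dates. SAP 9 and 14.2.1 impute partial dates that carry a year. The departure covers two classes: dates that are completely missing and dates without a year. SAP 9 is also not clear within itself. Its last sentence rules out imputation of safety data except partial or missing dates, which suggests that missing dates are imputed, but the sentence before says that they are not.

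**2. Run test onset dates through 14.2.1 and 10.6.** Assumed for illustration: first dose 10 September 2015, last dose 20 January 2016, no worsening date recorded. The TEAE window is then 10 September 2015 to 20 January 2016 + 30 days = 19 February 2016.

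| Onset as recorded | Imputed start | Inside the window? |
|---|---|---|
| Completely missing | none | cannot be tested |
| Day and month, no year | none | cannot be tested |
| 2015 only | 30 June 2015 | no, before first dose |
| September 2015 | 15 September 2015 | yes |
| October 2015 | 15 October 2015 | yes |

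The first two rows have no date to compare with first dose, so the definition cannot be met. In the third row the imputed month (June) differs from the month of first dose (September), so the adjustment does not apply. The same happens for any subject first dosed from 1 July onwards with a year-only onset in that year. Apart from a screening-procedure AE, such an event should not pre-date treatment, because collection had not begun.

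**3. Crossover.** Section 10.6 separates group 1 from group 3 by when the AE occurred. Without an onset date, nothing in the SAP settles the group.

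**4. Size.** A subject whose only record of a term is undated changes that term's incidence by 100/n percentage points:
- planned cohort, n = 20: 100/20 = 5.0
- n = 19, the figure used in the power calculation: 100/19 = 5.3
- smaller cohorts: more than this; the documents do not give the final cohort sizes.

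The number of AEs without a usable onset date is not in the documents.

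**The case against.** The strongest reply has four parts.

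- **The SAP does not say that undated AEs are excluded.** This is true. Exclusion comes from applying the definition as written, and a programmer could choose otherwise. The definition also accepts a worsening date, so an AE with a missing onset but a recorded worsening can qualify, and deaths are listed and summarised separately. The effect is therefore limited to AEs with neither date, and to tables built on TEAEs.
- **Such AEs should be rare.** Protocol 6.2.2 asks for start and end dates on every AE, 7.5 requires eCRFs within 5 days of a visit, 7.6 provides monitoring, and 6.2.4 requires SAE reports within 24 hours. This stands as a limit on the likely size. It does not supply a rule for the cases that remain.
- **The protocol left the detail to prespecified rules, and the SAP supplies them.** This holds for partial dates with a year and month. It does not hold for missing dates, which the protocol names and the SAP declines to impute.
- **The medication rule is not a model for counting an undated AE in both crossover groups.** This is right. That rule requires both dates to be missing, and the SAP expressly lets a medication be both prior and concomitant. The AE groups are mutually exclusive in time, so an AE should be counted once.

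A reader might go further and infer that reported AE incidence in this trial is biased downward. The documents do not support that: they record no undated AE, and the 5-point figure is the weight of one subject, not an observed effect.

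**Conclusion.** The conflict between Protocol 5.4 and SAP 9 and 14.2.1 is real and is not declared in SAP 12. As written, an AE with neither an onset nor a worsening date cannot be a TEAE and has no crossover group. A year-only onset can be dated before first dose in a subject who started treatment after June of that year. Both faults act in the anti-conservative direction, given that collection starts at first dose apart from screening-procedure AEs.

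The size is conditional: 5 percentage points per affected subject and term at 20 per cohort, more in smaller cohorts, and nothing if no such AE was recorded. The conclusion rests on a literal reading of 10.6 and on no default existing elsewhere in the SAP; none was found. It is a gap that should be closed because the remedy is cheap and the endpoint is primary. It is not evidence that the reported safety results are wrong.

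**What to change.** Make four changes.

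1. In SAP 10.6 and 14.2.1: an AE whose onset date is completely missing or lacks the year is treatment-emergent, unless its end date is before first dose or it was recorded as due to a screening procedure.
2. In SAP 14.2.1: apply the move to the first-dose date also to year-only onsets in the year of first dose, unless the end date is before first dose.
3. For crossed-over subjects: assign an undated AE to one group by a single stated rule. Use the end date where it settles the matter (an end before crossover means group 1). Otherwise use one prespecified default, with a flag in the listing. Do not count the event in both groups.
4. Record the departure from Protocol 5.4 in SAP 12. If version 2.0 is already final, record it in the CSR, where the SAP introduction says that changes to the planned analyses will be documented.

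The cost is a few sentences and a few programming conditions. The downside is that a rare event outside the TEAE window may be counted. For example, the follow-up visit may fall as late as 30 + 7 = 37 days after last dose, while the TEAE window closes at 30 days. The number of AEs classified by default should be given in a footnote so that the reader can judge this.
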